11.4 Data and Safety Monitoring

A Data and Safety Monitoring Committee will oversee the conduct of the study. The Committee consists of four members from outside of the SWOG, 3 SWOG members, 3 non-voting representatives from the National Cancer Institute (NCI), and the Group Statistician (non-voting). The members of this Committee will receive confidential reports every 6 months from the SWOG Statistical Center, and will meet at the Group's bi-annual meetings as necessary. The Committee will be responsible for decisions regarding possible termination and/or early reporting of the study.

11.5 Translational Medicine

The associations between each potential predictive biomarker ([Objectives 11.5a](#) and [11.5b](#) below) and PFS will be explored via Kaplan-Meier curves and Cox regression. For each arm, it is estimated that 42 (90% of) eligible patients will have usable samples submitted for these translational studies. Statistical power to assess treatment-biomarker interactions will be low; all such power calculations assume the baseline median PFS is 2.4 months, no treatment effect in the biomarker-negative subgroup, and a two-sided alpha of 0.05.

Objectives

- a. To evaluate low-frequency *KRAS* or *NRAS* mutations as detected by high-depth sequencing as a predictive biomarker of efficacy.
 1. Preliminary data is pending for *BRAF* mutant patients, but approximately 20% of *KRAS* wild type patients by standard of care testing will have detectable *KRAS* or *NRAS* on high-depth sequencing.
 2. Assuming that detectable *KRAS* or *NRAS* is present in 20% of patients, 84 patients would provide 74% power to detect an interaction hazard ratio of 5.0 between treatment and biomarker status (corresponding to a median PFS of 12.0 months in the vemurafenib arm for the biomarker positive subgroup).
- b. To evaluate PI3K pathway activation as a predictive biomarker of efficacy (PFS)
 1. Preliminary data in archival material from *BRAF* mutant, metastatic colorectal cancer tumors suggests that 60% of patients will have activation of the PI3K pathway, as defined by complete PTEN loss by IHC or PIK3CA mutation in the kinase or helical domains.
 2. Assuming that PI3K pathway activation is present in 60% of patients, 84 patients would provide 80% power to detect an interaction hazard ratio of 4.0 between treatment and biomarker status (corresponding to a median PFS of 9.6 months in the vemurafenib arm for the biomarker positive subgroup).
- c. To evaluate gene expression signatures from screened patients with *BRAF*^{WT} and *BRAF*^{V600E} tumors.
 1. This analysis will be very exploratory in nature. Analyzed gene signatures from tumor tissue will be described separately in patients with *BRAF*^{WT} (up to n=52, 90% of screen-negative patients) and *BRAF*^{V600E} (n=84, 90% of eligible patients). We will explore, but not limited to, associations between gene signatures and colorectal cancer oncogenesis, angiogenesis, immune pathways, PI3K, WNT, EGF, and MEK pathway signatures, epigenetic regulators, p53, NOTCH and TGF-beta signaling. The definitive list of genes and technologies might only be finalized after complete enrollment and will be based on scientific knowledge at that time.
- d. To provide validation of *BRAF* IHC using complementary sequencing methodology.
 1. Both *BRAF* and Cobas version 2.0 testing will be performed on screened patients (n=163). We will evaluate the sensitivity and specificity of *BRAF* IHC compared to the Cobas version 2.0 testing.

- e. To confirm the estimated sensitivity of detectable BRAF V600E circulating cell-free DNA as a non-invasive biomarker for BRAF V600E mutation as detected by IHC and Cobas in the primary tumor.
1. Unpublished results in 37 patients demonstrated 100% specificity and 78% sensitivity for the circulating cell-free DNA compared to the mutation assay on the primary tumor.
- f. To correlate radiographic tumor response with the change in quantification of BRAF V600E alleles in circulating cell-free DNA.
1. Analysis of plasma samples at baseline, during therapy, and at the time of progression across all arms (including Arm 3).
 2. No preliminary data are available for this aim.
 3. We will assess the relationship between RECIST radiographic assessment and change in BRAF V600E allele burden in the cfDNA via logistic regression.
- g. To monitor for known mechanism of acquired resistance to EGFR inhibition in circulating cell-free DNA (KRAS, NRAS mutations).
1. Analysis of plasma samples at baseline and at the time of progression on all arms (including progression on Arm 3).
 2. Preliminary data are not available for the BRAF population, but in a KRAS wild-type population, our preliminary data suggest that approximately 40% of patients develop new detectable mutations in KRAS, NRAS, or EGFR after treatment with cetuximab.
 3. Simple proportions with estimated 95% confidence intervals will be used to describe the observed incidence of new detectable mutations.
- h. To assess the correlation of treatment efficacy between patients and matched patient-derived xenograft (PDX) models.

The correlation between radiographic response in patients and reduction in tumor size in the corresponding PDX models receiving matched treatment will be assessed. Given a 67% success rate at MD Anderson in establishing PDXs using *BRAF*-mutated tumors, it is estimated that 12 PDXs will be established from the 18 tumor biopsies collected from either arm of **S1406**. For each PDX, 24 mice will be equally randomized into one of three arms: a control arm receiving placebo (C) or one of two treatment arms, irinotecan + cetuximab or irinotecan + vemurafenib + cetuximab. For each PDX, the mice will be assessed at Day 21. The average % reduction in tumor size will be compared between the mice receiving the treatment to which the corresponding patient had been randomized and the mice in the control arm receiving placebo. The treatment/ control ratio (%T/%C) will be calculated. To evaluate the association between the patient and corresponding xenograft model results, a Pearson correlation coefficient will then be estimated between %T/%C and the RECIST response of matched patients. 12 PDXs will have 80% power to detect a correlation coefficient of 0.712 at a two-sided 0.05 significance level.

In order to investigate further the correlation in raw tumor responses between the clinical and animal studies, a secondary analysis will model $\%T_{end}/T_{start}$ in the xenograft animals as a function of radiographic response according to RECIST criteria in matched patients via a linear mixed model.

- i. To assess the correlation between PDX mechanisms for resistance and circulating free DNA (cfDNA) in plasma samples of matched patients following progression of disease.

cfDNA will be extracted from plasma taken from pre-treatment and post-progression samples of patients whose tumors were used to establish PDX models. These samples will then be analyzed by ultra-deep next-generation sequencing for the full exons of 15 genes (including KRAS, NRAS, EGFR, and MEK) and hotspot coverage for an additional 36 genes of interest. McNemar's test will be used to compare the mutation status of cfDNA before treatment and after progression for each gene of interest. We will adjust for multiple comparisons using methods described by Benjamin-Hochberg. (49) The concordance (i.e. proportion of the status unchanged, with 95% CI) of acquired mutation status between patient plasma samples and corresponding PDX models for each gene will be estimated. If concordance of PDX with matched patient in 6 of 12 pairs is observed, then the estimated half length of the 95% CI will be 0.25.

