1.4 Translational Objectives

- a. To evaluate genetic alterations, including low-frequency *KRAS* or *NRAS* mutations (definitive list of genes to be finalized after completion of enrollment based on latest scientific knowledge) as detected by high-depth sequencing as predictive biomarkers of efficacy.
- b. To evaluate PIK3CA pathway activation through PIK3CA mutations or PTEN protein loss as a predictive biomarker of innate resistance to this regimen.
- c. To evaluate gene expression signatures from screened patients with BRAF^{WT} and BRAF^{V600E} tumors.
- d. To provide validation of BRAF IHC using complementary sequencing methodology from screened patients with BRAF^{WT} and BRAF^{V600E} tumors.
- e. To confirm the estimated sensitivity of detectable BRAF V600E circulating cell-free DNA as a non-invasive biomarker for BRAF V600E mutation as detected by IHC in the primary tumor.
- f. To correlate radiographic tumor response with change in quantification of BRAF V600E alleles in circulating cell-free DNA.
- g. To monitor for known mechanism of acquired resistance to EGFR inhibition in circulating cell-free DNA.
- h. To assess the correlation of treatment efficacy between the patients and the matched patient-derived xenograft (PDX) models.
- i. To assess the correlation between PDX mechanisms for resistance and circulating free DNA (cfDNA) in plasma samples of matched patients following progression of disease.

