11.2 Primary Analysis and Power Justification

The primary analysis of PFS among patients randomized to Arm 1 or Arm 2 will be conducted in all eligible patients according to the intent-to-treat principle, using the log rank test upon the observation of 88 PFS events. Patients will be stratified by prior treatment with irinotecan. There are no randomized second or third line studies that have reported outcomes with cetuximab and irinotecan specifically for the population of patients with BRAF mutations. However, a retrospective study of 75 patients with BRAF mutant tumors demonstrated progression-free survival of 2.4 and 2.3 months for second and third line regimens, respectively. (*in press, Clinical Colorectal Cancer*) Therefore, we estimate the median Progression-Free Survival (PFS) of patients treated with Cetuximab and Irinotecan to be 2.4 months (null hypothesis) in this study population. Assuming that the targeted agent offers an increase of 2.4 months in PFS for this population (HR 2.0), we will need 94 eligible patients, based on six months of follow-up, a two-sided type 1 error of 5% and 90% power.

An interim analysis will be performed when one-half of the events (approximately 44 PFS failures) have been observed (anticipated to occur when approximately 60% of accrual is reached). Evidence suggesting early termination would consist of a PFS hazard ratio > 1.0 comparing the experimental arm to the control arm, as estimated by a Cox regression model. This rule yields a 50% likelihood of terminating the study under the null hypothesis. Unless there are toxicity concerns, the study will not close during this interim assessment.

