18.2 Translational Medicine

a. Background

Loss of PTEN and activating mutations in the *PIK3CA* oncogene result in activation of PI3K/Akt signaling, a pathway implicated in anti-apoptotic activity. When compared to melanoma, *BRAF* mutant CRCs have higher PI3K pathway activity due to both genetic (PTEN, *PIK3CA*, *PIK3R1*) and epigenetic (hypermethylation) mechanisms. (28) Comparative studies between *BRAF*-mutated melanoma and colorectal cell lines by reverse phase protein arrays suggest that the colon cell lines have much higher rates of PI3K pathway activation, as reflected by significant differences in pAkt, pMTOR, pFoxo3A, pGSK3b, pS6, and p4EBP expression. Those lines harboring *PIK3CA* gene mutations or loss of PTEN are less sensitive to *BRAF* inhibition than cell lines expressing PTEN and lacking mutations in *PIK3CA*. Additionally, when cell lines with intact PTEN were introduced with siRNA against PTEN, cytotoxic activity of vemurafenib was lost. These results imply that, in the presence of *BRAF* inhibition, molecular aberrations like PTEN loss or activating *PIK3CA* mutations, which increase signaling of the PI3K/Akt pathway, decrease sensitivity to *BRAF* inhibition. Therefore, we hypothesize that patients whose tumors contain activating *PIK3CA* mutations or show loss of PTEN immunohistochemically will demonstrate no benefit in progression-free survival with the addition of vemurafenib, relative to patients whose tumors do not harbor such alterations.

NRAS mutations and *KRAS* mutations outside of codons 12 and 13 have been identified as a potential predictive biomarker of resistance to cetuximab, and we propose to include this in the testing, recognizing a potential shift in clinical practice during the course of the study.

Data on the utility of circulating DNA for monitoring treatment response and development of resistance have previously been reported. (30-32) Unpublished results using mice implanted with patient-derived *BRAF*-mutated colorectal tumors and treated with a *BRAF* inhibitor have shown that *NRAS* and *KRAS* mutations may develop as a mechanism of resistance to *BRAF* inhibition in *BRAF*-mutated CRC and the concurrent use of EGFR inhibitors suggests that *KRAS* mutations may likewise occur. (33)

b. Experimental Approach, validated assays employed and expertise of PI:

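### Does section 11.5b.2 power the PI3K interaction in the wrong direction, and does that call for a change?

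*Combined protocol and SAP*

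**What the plan says.** The opening paragraph of section 11.5 says that the association of each potential predictive biomarker with PFS "will be explored via Kaplan-Meier curves and Cox regression". It warns that interaction power will be low and sets shared assumptions for all the interaction calculations: a baseline median PFS of 2.4 months, "no treatment effect in the biomarker-negative subgroup", and a two-sided alpha of 0.05.

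Objective b.2 then begins "Assuming that PI3K pathway activation is present in 60% of patients" and gives 80% power, with 84 patients, for an interaction hazard ratio of 4.0, "corresponding to a median PFS of 9.6 months in the vemurafenib arm for the biomarker positive subgroup".

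Two other sections give the expected direction. Section 1.4b treats PI3K activation "as a predictive biomarker of innate resistance to this regimen". Section 18.2a reports cell-line evidence that such alterations, "which increase signaling of the PI3K/Akt pathway, decrease sensitivity to" BRAF inhibition, and hypothesizes that patients who carry them "will demonstrate no benefit in progression-free survival with the addition of vemurafenib, relative to patients whose tumors do not harbor such alterations".

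Section 11.2 sets the overall planning effect: "Assuming that the targeted agent offers an increase of 2.4 months in PFS for this population (HR 2.0").

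**The concern.** Read together, the shared assumptions and 11.5b.2 give a fourfold gain to the PI3K-activated 60% and nothing to the PI3K-intact 40%. That is the reverse of 1.4b and 18.2a. Section 11.5b.2 is also the only place where the size of the PI3K effect is quantified.

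Three things could be at stake:

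- The stated 80% might not apply to the effect that the investigators actually expect, since the benefit would then fall in the smaller group.
- The record might allow either direction to be presented later as the planned one.
- An interaction compares two effects. It does not by itself show whether activated patients gain nothing, and no section says in so many words that the Arm 2 versus Arm 1 hazard ratio will be reported within each PI3K group.

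**Working it through.** **Inputs.** From 11.5: 42 patients per arm with usable samples (84 in all), control median 2.4 months, PI3K activation in 60%, interaction hazard ratio 4.0, two-sided 0.05. From 11.1 and 11.2: 26 months of accrual and 6 months of follow-up. The documents give no further detail for the interaction calculation, so exponential PFS, uniform accrual and no dropout are assumptions here.

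**Planning hazard ratios in each group.** Biomarker-positive: 9.6 / 2.4 = 4.0. Biomarker-negative: 1.0, from the stated absence of effect. Their ratio is 4.0, which matches the stated interaction. Both planning values therefore follow from the text.

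**Cell sizes.** Per arm, 0.6 × 42 = 25.2 activated and 0.4 × 42 = 16.8 intact.

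**Event probability.** With rate λ = ln 2 / median, accrual A = 26 and follow-up F = 6,

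p = 1 − [exp(−λF) − exp(−λ(A+F))] / (λA).

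This gives p = 0.976 for a median of 2.4 months and p = 0.707 for 9.6 months.

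**Closed-form power.** SE = √(Σ 1/d) over the four arm-by-PI3K cells, and power = Φ(ln 4 / SE − 1.96), with ln 4 = 1.386.

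| Scenario | Events: control activated, Arm 2 activated, control intact, Arm 2 intact | SE | ln 4 / SE | Power |
|---|---|---|---|---|
| As printed (benefit in activated) | 24.6, 17.8, 16.4, 16.4 | 0.468 | 2.965 | 84.2% |
| Reversed (benefit in intact, as in 18.2a) | 24.6, 24.6, 16.4, 11.9 | 0.476 | 2.914 | 83.0% |

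**Simulated Cox model** with arm, PI3K and their product (8,000 trials, Wald test): 81.5% as printed and 81.1% reversed. A separate run of 4,000 trials per scenario with fixed cell sizes gave 81.9% and 82.9%. The plan's 80% is therefore reproduced to within about 2 to 4 points, and the direction moves it by about 1 point at most.

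**Sensitivity to follow-up.** If the analysis came at the end of accrual with no further follow-up (F = 0), the closed form gives 78.3% as printed and 76.3% reversed. Follow-up matters more than direction.

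**Why direction matters so little.** Reversal only changes which Arm 2 cell loses events to the longer median. Moving the 9.6-month median from a cell of 25.2 patients to one of 16.8 changes the SE from 0.468 to 0.476. A two-sided test has no preferred sign.

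**Consistency with 11.2.** Averaged on the log scale by prevalence, the printed scenario implies an overall ratio of 4^0.6 = 2.30 and the reversed one 4^0.4 = 1.74, against 2.0 in 11.2. Neither equals 2.0, so rewording would not align this calculation with the primary design either.

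**Hazard ratio within each PI3K group.** Code PI3K as 1 for activated. In a Cox model with arm, PI3K and their product, the arm coefficient is the log hazard ratio in intact patients, and arm plus product is the log hazard ratio in activated patients. No extra model or data are needed.

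**The case for a change.** The strongest case for a change is that the contradiction is plain and cheap to correct. Nothing in 11.5b.2 defines biomarker-positive as PI3K-intact, and activation is the only state with a prevalence. A reader who relied on 11.5b.2 alone would take the planned effect to be the opposite of the trial's rationale. That mismatch stands. It does not leave the direction open, though, because the objective in 1.4b and the hypothesis in 18.2a both state it explicitly, and 11.5b.2 adds only a size for a power calculation. The wording looks like a shared template: 11.5a also places the whole benefit (12.0 months) in the biomarker-positive group, although 18.2a discusses RAS mutations as markers of resistance.

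It can also be argued that a significant interaction may arise while activated patients still gain something, so that the estimate within that group is what addresses the absence of benefit in 18.2a. As a point about interpretation this is correct. It does not reveal an omission that would go unfilled. Section 11.5 already plans Kaplan-Meier curves and Cox regression and refers to treatment-biomarker interactions. An analyst fitting that model would report the hazard ratio in each group as a matter of course. The caution about precision is also there in substance, since 11.5 calls the work exploratory and the power low.

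**Conclusion.** The power scenario in 11.5b.2 does run opposite to 1.4b and 18.2a, and this is a clerical slip in the description of a planning scenario. With 6 months of follow-up, the two-sided interaction power is about 81 to 84% in either direction against the stated 80%. With no follow-up after accrual it is about 76 to 78% by closed form, again nearly the same both ways. These figures assume exponential PFS, uniform accrual and no dropout.

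Correcting the direction would alter no sample size, test, stated power or conclusion, and the objective is exploratory and separate from the primary analysis. The planning hazard ratios in each group (4.0 and 1.0) follow from the text, and the estimated ones come from the planned Cox model. No change to the plan is needed.

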10.2 Objective Status at Each Disease Evaluation

Objective Status is to be recorded at each evaluation. All measurable lesions up to a maximum of 2 lesions per organ 5 lesions in total, representative of all involved organs, should be identified as *target* lesions at baseline. All other lesions (or sites of disease) including any measurable lesions over and above the 5 target lesions should be identified as *non-target* lesions. Measurements must be provided for target measurable lesions, while presence or absence must be noted for non-target measurable and non-measurable disease.

For studies that use disease progression as an endpoint, whole body scanning at specific intervals is necessary to determine that progression is NOT present outside of the "target" areas. Therefore, in these studies it is not acceptable to image only the "target" areas of the body in follow-up scans. For study-specific imaging requirements, see the Study Calendar in [Section 9.0](#).

- a. **Complete Response (CR):** Complete disappearance of all target and non-target lesions (with the exception of lymph nodes mentioned below). No new lesions. No disease related symptoms. Any lymph nodes (whether target or non-target) must have reduction in short axis to < 1.0 cm. All disease must be assessed using the same technique as baseline.
- b. **Partial Response (PR):** Applies only to patients with at least one measurable lesion. Greater than or equal to 30% decrease under baseline of the sum of appropriate diameters of all target measurable lesions. No unequivocal progression of non-measurable disease. No new lesions. All target measurable lesions must be assessed using the same techniques as baseline.
- c. **Stable:** Does not qualify for CR, PR, Progression or Symptomatic Deterioration. All target measurable lesions must be assessed using the same techniques as baseline.
- d. **Progression:** One or more of the following must occur: 20% increase in the sum of appropriate diameters of target measurable lesions over smallest sum observed (over baseline if no decrease during therapy) using the same techniques as baseline, as well as an absolute increase of at least 0.5 cm. Unequivocal progression of non-measurable disease in the opinion of the treating physician (an explanation must be provided). Appearance of any new lesion/site. Death due to disease without prior documentation of progression and without symptomatic deterioration (see [Section 10.2e](#)).

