11.3 Other Analyses

Secondary endpoints will include overall survival, response, and toxicity. Distributions of overall survival in Arms 1 and 2 will be estimated using the method of Kaplan-Meier. The overall response rate (confirmed and unconfirmed, complete and partial) in each treatment arm will be assessed in the subset of patients with measurable disease. Assuming 90% (n=42 per arm) of patients will present with measurable disease, response rate can be estimated to within 16% (95% confidence interval).

Patients receiving at least one dose of drug on any arm will be included in the assessment of adverse events. Adverse event monitoring is conducted by the study chairs, disease committee chair, Adverse Event Coordinator and study statistician on an ongoing basis, with notification to the DSMC and CTEP should any concerns arise. Any events reported through the CTEP-AERS system are reported immediately, and reports are sent to the above group for all other AEs on a monthly basis. This trial will employ especially careful adverse event monitoring for the first 14 patients randomized to vemurafenib (Arm 2). Rates of serious toxicities will be compared between Arms 1 and 2 after 3, 6, and 14 patients are assigned to Arm 2 and have completed the first cycle, to inform discussions of protocol modification or early closure if required. Forty-seven eligible patients in each arm are sufficient to estimate the probability of a particular toxicity to within 15% (95% confidence interval). Any toxicity occurring with at least an 8% probability is likely (98% chance) to be seen at least once.

Patients progressing on Arm 1 will be provided the opportunity to cross over to vemurafenib treatment on Arm 3. Overall survival, response and PFS among patients who register to Arm 3 after disease progression will be summarized using descriptive statistics as described above.

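### The 11.5f analysis relates cfDNA change to RECIST categories only; adding a continuous tumor-size analysis from measurements already collected would be a cheap gain whose size depends on choices the plan leaves open

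*Combined protocol and SAP*

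**What the plan says.** Section 1.4f states the aim: "To correlate radiographic tumor response with change in quantification of BRAF V600E alleles in circulating cell-free DNA". Section 11.5f repeats it and names the method in item 3: "We will assess the relationship between RECIST radiographic assessment and change in BRAF V600E allele burden in the cfDNA via logistic regression". Item 1 places plasma samples at baseline, during therapy and at progression, on all arms including Arm 3. Item 2 adds: "No preliminary data are available for this aim".

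The section does not say which RECIST categories form the outcome, whether the logistic model is binary or ordinal, or which time point counts. It gives no power, sample size or expected correlation for this aim.

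Section 10.2, on recording status at each disease evaluation, says: "Measurements must be provided for target measurable lesions". Section 11.3 plans on "Assuming 90% (n=42 per arm) of patients will present with measurable disease". The calendars in 9.1 to 9.3 put blood and imaging together at Week 9, and Section 15.3 takes plasma at each restaging.

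**The concern.** The aim concerns a quantitative change in allele burden, but the tumor side is used only as a category. Under the Section 10.2 cut-points (a decrease of at least 30% for partial response; a 20% increase plus an absolute increase of 0.5 cm for progression), a target sum that shrinks by 28% and one that grows by 15% can both be stable. In a responder/non-responder split they also count the same. The continuous measure can be derived from data that sites already submit for patients with measurable disease.

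Nothing in the documents gives a reason to use categories alone here. RECIST status is needed for PFS and response rate, but this aim is neither. The neighboring aim 11.5h plans a Pearson correlation and a linear mixed model for a related radiographic question.

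This is the plan's only analysis of cfDNA change as a marker of tumor response, and it starts without preliminary data. What is at stake is the precision of a first estimate. Leaving the outcome coding and time point open also lets them be settled after the data are seen.

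**Working it through.** **Is there a figure to reproduce?** Section 11.5f has none. The nearest is in 11.5h: 12 pairs, correlation 0.712, two-sided 0.05, stated power 80%. Simulating the Pearson test gives 80.1%, so the method agrees with the plan's own.

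**Sample sizes from the documents.**
- Section 11.5: "For each arm, it is estimated that 42 (90% of) eligible patients will have usable samples submitted for these translational studies". 0.9 × 94 = 84.6, taken as 84.
- With measurable disease (11.3), assuming independence: 84 × 0.9 = 75.6, about 76.
- Section 11.5e reports "100% specificity and 78% sensitivity for the circulating cell-free DNA" against the tumor assay. Taking 78% as the share with quantifiable baseline cfDNA: 76 × 0.78 = 59.3, about 59. Without the measurability restriction: 84 × 0.78 = 65.5, about 66.

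**Assumed, because the documents are silent.** True correlation ρ between log cfDNA change and tumor change; responder share; bivariate normality; one sample pair per patient; two-sided 0.05 (stated in 11.5 for the interaction calculations only).

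**Comparison at equal n.** Simulated power (%) of the Pearson/linear test, of binary logistic regression (likelihood-ratio test) by responder share, and of an ordinal analysis:

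| n | ρ | Continuous | 10% | 20% | 30% | 50% | Ordinal |
|---|---|---|---|---|---|---|---|
| 76 | 0.3 | 74 | 33 | 45 | 53 | 57 | 66 |
| 76 | 0.4 | 95 | 56 | 72 | 79 | 84 | 91 |
| 76 | 0.5 | 100 | 75 | 89 | 94 | 97 | 99 |
| 59 | 0.4 | 89 | 43 | 62 | 68 | 73 | 79–83 |

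Loss = continuous minus logistic. For n = 76, ρ = 0.3: 74 − 33 = 41, 74 − 45 = 29, 74 − 53 = 21 and 74 − 57 = 17 points (binary); 74 − 66 = 8 (ordinal). For n = 59, ρ = 0.4: 46, 27, 21 and 16 points (binary). Repeat runs differ by up to about three points.

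**Wider grid** (n = 59, 66, 76, 84; 10% to 35% responders; Wald and likelihood-ratio tests):
- Binary loss: 10–30 points at ρ = 0.2, 20–48 at 0.3, 13–52 at 0.4, 3–44 at 0.5, 0–29 at 0.6.
- For ρ from 0.2 to 0.4, 90% (Wald) to 93% (likelihood ratio) of scenarios lie within 15–45 points. Over ρ from 0.2 to 0.6 only 65–67% do.
- Ordinal loss (three or four categories): 4–14 points for ρ from 0.2 to 0.4, and 0–4 points at 0.5 or more.

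**Unequal n.** The logistic model can also use patients with non-measurable disease. At ρ = 0.3 and 20% responders, continuous on 76 has 74% power and binary logistic on 84 has 47% (Wald) or 51% (likelihood ratio). The loss is 74 − 47 = 27 or 74 − 51 = 23 points, against 32 or 29 when both use 84.

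**When the target sum is not the whole response.** Let cfDNA correlate 0.4 with overall response, let the target sum track overall response with correlation τ, and assume 40% progressors. The correlation between cfDNA and the target sum is then 0.4τ.
- τ = 0.85: 0.4 × 0.85 = 0.34. Linear on 59 has 77% power; binary logistic (progression yes/no) on 66 has 77%; a three-category rank test has 83%.
- τ = 0.7: 0.4 × 0.7 = 0.28. Linear has 58%, against 77% and 83%.
- τ = 1: linear gains 13 points over binary and 6 over ordinal.

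**The case against.** The strongest objection is that RECIST status is more than a coarse copy of the target sum. Under Section 10.2 any new lesion, or unequivocal progression of non-measurable disease, is progression. If cfDNA reflects total tumor burden, the category holds information that the sum lacks. The τ calculation shows that the continuous gain can then vanish or reverse. This stands. It is why the RECIST model should be kept at full standing and not replaced.

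The text also never says responder versus non-responder. Section 10.2 lists ordered statuses, so an ordinal logistic model fits the wording and costs little. This stands too. A reader might infer that the plan as written loses 15 to 45 points. The documents do not support that without the added assumptions of a binary split and a modest correlation.

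A reader might also infer that a moderate correlation would probably be missed. At ρ = 0.4 and n = 59, binary logistic power is 62% to 73% with 20% to 50% responders, so detection is more likely than not. It is below one half at 10% responders, or generally at ρ = 0.3 with this n, and the documents establish neither condition.

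Finally, making first restaging the main time point has a price. Imaging is every 8 weeks, about 1.84 months. With the assumed control median of 2.4 months and exponential PFS, 1 − 0.5^(1.84/2.4) = 41% of controls have an event by then. Those who died or deteriorated without a scan have no target sum, and that loss may be informative. This limits the continuous analysis but does not argue against adding it.

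**Conclusion.** The point holds as a conditional, low-cost improvement. Section 11.5f.3 uses radiographic response only as RECIST categories, although target-lesion measurements exist for the roughly 90% of patients expected to have measurable disease. At equal n the cost is about 15 to 45 points of power if the outcome is responder/non-responder and ρ is about 0.2 to 0.4. It is about 4 to 14 points with an ordinal model, often smaller at ρ of 0.5 or more, and possibly nil if new or non-target lesions carry much of the response.

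These sizes rest on assumed correlations and responder shares, bivariate normality and one pair per patient. Repeated samples, and the reuse of Arm 1 patients on Arm 3, were not modeled. The aim is exploratory and claims no power, so no figure in the plan is wrong. Asking whether cfDNA change tracks RECIST status remains a legitimate question.

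**What to change.** Add to 11.5f.3:

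> In patients with measurable disease, percent change from baseline in the sum of target-lesion diameters will also be related to log change in cfDNA BRAF V600E allele burden by linear regression (Spearman correlation if clearly non-normal), adjusted for treatment arm, with the first restaging as the main time point for this continuous analysis. The RECIST assessment will be analyzed alongside by logistic regression that keeps the ordered categories, including patients with non-measurable disease or progression by new or non-target lesions. Later on-therapy, progression and Arm 3 samples remain in the analysis as planned in 11.5f.1. The number of patients without a first-restaging scan will be reported by arm.

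The cost is a few sentences and a little analysis time, with no new scans, samples or visits. The continuous analysis omits about 10% of patients (non-measurable disease) and those with no scan at first restaging, and it does not see new-lesion progression. The RECIST model kept alongside covers non-measurable disease and new-lesion progression. The missing-scan group is not recovered, so its size must be shown.
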